15.3 Data Quality Control and Reporting.....	30
15.4 Archival of Data.....	30
15.5 Availability and Retention of Investigational Records.....	30
15.6 Monitoring	31
15.7 Subject Confidentiality	31
16 ADMINISTRATIVE, ETHICAL, REGULATORY CONSIDERATIONS	31
16.1 Protocol Amendments.....	31
16.2 Institutional Review Boards and Independent Ethics Committees.....	31
16.3 Informed Consent Form.....	32
16.4 Publications.....	32
16.5 References.....	33

LIST OF ABBREVIATIONS

AE	adverse event
ALT	alanine aminotransferase
AST	aspartate aminotransferase
BUN	blood urea nitrogen
CFR	Code of Federal Regulations
CRF	case report form
FDA	Food and Drug Administration
GCP	Good Clinical Practice
HIPAA	Health Insurance Portability and Accountability Act of 1996
ICF	informed consent form
ICH	International Conference on Harmonisation
IEC	Independent Ethics Committee
IRB	Institutional Review Board
IV	intravenous
PI	Principal Investigator
PK	pharmacokinetic
SAE	serious adverse experience
SGOT	serum glutamic oxaloacetic transaminase
SGPT	serum glutamate pyruvate transaminase

PROTOCOL SYNOPSIS

TITLE	Clearance of 25-hydroxyvitamin D ₃ during vitamin D ₃ supplementation
SPONSOR	[name], MD, MS
FUNDING ORGANIZATION	National Institute of Diabetes and Digestive and Kidney Diseases (R01DK099199)
NUMBER OF SITES	Single-site study
RATIONALE	
Vitamin D clearance is an important and often overlooked aspect of vitamin D biology that has relevant implications for the clinical assessment and treatment of vitamin D deficiency. The circulating concentration of 25-hydroxyvitamin D [25(OH)D] is the most widely accepted measure of vitamin D status, and vitamin D supplements are often prescribed and titrated based on 25(OH)D concentration. However, circulating concentrations of 25(OH)D are necessarily determined by both 25(OH)D production and 25(OH)D clearance. Therefore, 25(OH)D clearance likely plays an important role in the assessment of vitamin D status and the response to vitamin D supplementation.
 
The goal of this study is to determine how 25(OH)D₃ clearance is affected by vitamin D₃ supplementation using a gold standard pharmacokinetic approach. We expect that this study will enhance interpretation of available diagnostic tests, inform the results of ongoing large clinical trials of vitamin D supplements, and help develop new strategies to target vitamin D to improve health.

STUDY DESIGN	
This is a single-dose, open-label pharmacokinetic study that uses intravenous administration of a stable deuterium-labeled 25(OH)D₃ to evaluate the metabolic clearance of 25(OH)D₃ in subjects that supplement their diet with vitamin D₃. These data will be compared with previously acquired “un-supplemented” measurements obtained from the same patients. This study will only enroll subjects who previously participated in the CLEAR or CLEAR-CF protocol and from whom un-supplemented measurements of 25(OH)D₃ clearance were obtained. The CLEAR and CLEAR-CF protocols are both included under IND 115016. In this study, a repeat measurement of 25(OH)D₃ clearance will be obtained from eligible subjects who are supplementing their diet with a stable dose of Vitamin D₃, defined as cholecalciferol 2000 IU daily. The patterns of 25(OH)D₃ clearance in these patients, with and without vitamin D₃ supplementation, will be assessed.

	
Allocation: Non-Randomized
 
Intervention Model: Single Group Assignment
 
Masking: Open Label

PRIMARY OBJECTIVE	The goal of this study is to determine if 25(OH)D ₃ clearance is affected by vitamin D ₃ supplementation.
SECONDARY OBJECTIVES	
 • To explore whether disease status (chronic kidney disease or cystic fibrosis) modify the 25(OH)D₃ clearance response to vitamin D₃ supplementation. • To evaluate biomarkers of 25(OH)D₃ clearance during vitamin D₃ supplementation.
NUMBER OF SUBJECTS	Up to 20
SUBJECT SELECTION CRITERIA	
Inclusion Criteria:
 
 • Successful completion of related protocol CLEAR or CLEAR-CF, defined as: 
 ○ Previous administration of D₆-25-hydroxyvitamin D₃ Solution under the CLEAR or CLEAR-CF protocol, ○ Completion of at least 7 CLEAR or CLEAR-CF study visits, and ○ Absence of adverse events related to D₆-25-hydroxyvitamin D₃ Solution administration during participation in CLEAR or CLEAR-CF 
Exclusion Criteria:
 
 • Primary hyperparathyroidism • Gastric bypass • Tuberculosis or sarcoidosis • Current pregnancy • Child-Pugh Class B or C cirrhosis (i.e. cirrhosis with ascites, hepatic encephalopathy, bilirubin \geq 2 mg/dL, serum albumin \leq 3.5 g/dL, or PT \geq 4 seconds) • History of kidney transplantation (unless failed transplant now treated with hemodialysis) • Use of 1,25(OH)₂D₃ or an analogue, calcimimetics, or medications known to induce CYP24A1 within 4 weeks (wash-out allowed) • Serum calcium > 10.1 mg/dL • Hemoglobin < 9 g/dL
TEST PRODUCT, DOSE, AND ROUTE OF ADMINISTRATION	We will administer D ₆ -25-hydroxyvitamin D ₃ Solution for Injection, 20 µg/mL intravenously. The deuterated 25(OH)D ₃ is formulated using cosolvents to enhance solubility. Each mL contains 20 µg D ₆ -25(OH) D ₃ , 60% propylene glycol, 10% ethanol (ETOH) and water (30%) for injection, to volume. To

	ensure reliable detection of circulating deuterated 25(OH)D ₃ , without administering a dose that might alter the underlying vitamin D metabolism, we aim to administer a dose that results in a peak deuterated 25(OH)D ₃ concentration of approximately 5 ng/mL. The administered dose will be calculated as the targeted peak serum deuterated 25(OH)D ₃ (5 ng/mL) multiplied by blood volume.
CONTROL PRODUCT, DOSE AND ROUTE OF ADMINISTRATION	There is no control product.
DURATION OF SUBJECT PARTICIPATION AND DURATION OF STUDY	Subjects will be on study for approximately 6 months Screening and vitamin D₃ supplement run-in: 3 months Re-screening and scheduling: approximately 1 month Treatment: 1 day (subjects to the University of Washington Clinical Research Center) Follow-up: 8 weeks The total duration of the study is expected to be up to 18 months for subject recruitment and an additional 12 weeks for final subject follow-up.
CONCOMITANT MEDICATIONS	Required: 
 Vitamin D₃ (cholecalciferol) 2000 IU daily by mouth from start of run-in through completion of follow-up, provided by study team Allowed: 
 Additional vitamin D supplements (cholecalciferol or ergocalciferol, alone or contained in multivitamins) not to exceed a mean daily dose of 400 IU Prohibited (from 4 weeks prior to D ₆ -25-hydroxyvitamin D ₃ until completion of the study): 
 1,25(OH)₂D₃ or an analogue (e.g. paricalcitol, hectorol) Calcimimetics (e.g. cinaclacet) Medications known to potently induce or inhibit CYP24A1 or CYP3A4
EFFICACY EVALUATIONS	None
PRIMARY ENDPOINT	
 Metabolic clearance of labeled 25(OH)D₃ (administered dose/AUC)
SECONDARY ENDPOINTS	
 AUC of labeled 25(OH)D₃ Terminal half-life of labeled 25(OH)D₃

	
 Volume of distribution in the central compartment of labeled 25(OH)D₃
OTHER EVALUATIONS	Metabolic formation clearance (metabolite/parent AUC ratio) for metabolites of labeled 25(OH)D ₃
SAFETY EVALUATIONS	Change in the serum concentrations of calcium, creatinine, AST, and ALT and from baseline to 7 days after 25(OH)D ₃ administration Incidence of adverse events
PLANNED INTERIM ANALYSES	This is not a clinical trial with an efficacy outcome, and it is neither randomized nor blinded. Formal interim analyses are not planned.
STATISTICS Primary Analysis Plan	We will compare the distribution of D ₆ -25(OH)D ₃ clearance measured during this study to the distribution of D ₆ -25(OH)D ₃ clearance measured in the same participants in the un-supplemented state during CLEAR or CLEAR-CF. We will use the paired t-test to test differences in these distributions. We will use linear regression with multiplicative interaction terms to explore whether CKD or CF modify the D ₆ -25(OH)D ₃ clearance response to vitamin D ₃ supplementation.
Rationale for Number of Subjects	With 20 participants, we can detect differences in D ₆ -25(OH)D ₃ clearance that are small (17.5-55 mL/min depending on assumptions) compared to the mean value observed in CLEAR (351 mL/min) and compared to the change in clearance we expect based on preliminary data (>50%).

1 BACKGROUND

Vitamin D supplementation improves bone mineral density, helps prevent fracture in high-risk populations, and may promote other aspects of health.¹ The broad potential health benefits of vitamin D are currently being tested in large clinical trials, such as the Vitamin D and Omega-3 Trial (VITAL). Circulating concentrations of 25-hydroxyvitamin D [25(OH)D] are currently the most widely accepted tool used to gauge the need for and response to vitamin D supplements. However, large inter-individual differences in circulating 25(OH)D concentration and the 25(OH)D response to vitamin D supplementation are well documented. Furthermore, 25(OH)D is itself relatively inactive, and circulating 25(OH)D concentrations reflect only substrate available for conversion to the 1,25-dihydroxyvitamin D [1,25(OH)₂D], the active vitamin D hormone.

Vitamin D clearance is an important and often overlooked aspect of vitamin D biology. Known clinical determinants of circulating 25(OH)D concentration, including dietary intake, sun exposure, adiposity, and race, focus almost entirely on vitamin D intake/production. These factors explain a minority of variability in circulating 25(OH)D concentration and the response to vitamin D supplementation. By definition, steady-state circulating concentrations of 25(OH)D are determined by both intake/production and clearance. Genetic heterogeneity in CYP24A1, the cytochrome P450 enzyme primarily responsible for 25(OH)D clearance, is also a known determinant of circulating 25(OH)D concentration. Our preliminary data suggest that vitamin D supplementation induces CYP24A1-mediated 25(OH)D clearance, and that kidney function may be an important determinant of the 25(OH)D clearance response to vitamin D supplementation.

The proposed studies will provide insight into the biology of 25(OH)D clearance that is likely to enhance interpretation of available diagnostic tests, inform the results of ongoing large clinical trials of vitamin D supplements, and help develop new strategies to target vitamin D to improve health.

1.1 Overview of Clinical Studies

Deuterated and tritiated 25(OH)D₃ have been used previously to study metabolism of vitamin D₃ in humans.²⁻⁶ In addition deuterium is has been used extensively to study metabolism and is considered safe.⁷

[figure not shown]
2 STUDY RATIONALE

Vitamin D may promote health through pleiotropic actions. Traditionally understood as a calcium regulatory hormone, 1,25-dihydroxyvitamin D (1,25(OH)₂D, the potent hormonal form of vitamin D) binds to its target receptor to regulate the transcription of hundreds of genes.¹⁻⁸ Vitamin D receptors are present in all nucleated cells in the body, and activation of vitamin D receptors modulates cellular processes related to proliferation, differentiation, fibrosis, cancer, cardiovascular diseases, and other chronic diseases.⁶⁻¹⁰ For each of these processes, large effects have been demonstrated in cell culture and animal-experimental models, and clinical epidemiology studies have observed associations of circulating vitamin D metabolite concentrations with clinical health outcomes. As an example, for cardiovascular diseases, 1,25(OH)₂D and analogues promote nitric oxide-mediated endothelial vasodilation,¹¹⁻¹⁶ down-regulate vascular smooth muscle cell proliferation and migration into the intima,¹⁷ inhibit osteogenic differentiation of vascular smooth muscle cells,¹⁸ inhibit macrophage cholesterol uptake and foam cell formation,¹⁹⁻²¹ promote a shift from atherogenic Th1 to anti-atherogenic

Th2 lymphocytes,²² reduce the development and progression of ventricular hypertrophy,²³⁻²⁷ mitigate cardiac fibrosis,²⁷⁻³⁰ and suppress the renin-angiotensin system in animal-experimental models.³¹⁻³³ Cardioprotective biological actions of vitamin D are further supported by associations of low serum 25-hydroxyvitamin D [25(OH)D] and 1,25(OH)₂D concentrations with clinical hypertension, myocardial infarction, stroke, left ventricular hypertrophy, cancer, and mortality.³⁴⁻⁴⁶ The totality of evidence for vitamin D has motivated large clinical trials, currently underway, to test whether vitamin D treatment will reduce the risks of cancer, cardiovascular disease, and other clinical health outcomes in the general population.

Inter-individual differences in serum 25(OH)D concentration and the serum 25(OH)D response to vitamin D supplements are large. The circulating concentration of 25(OH)D is widely accepted as a biomarker of total intake of vitamins D₃ and D₂ (cholecalciferol and ergocalciferol) from cutaneous synthesis and dietary consumption.¹⁻³ Serum or plasma 25(OH)D concentration increases robustly to vitamin D supplementation or exposure to ultraviolet light. Circulating 25(OH)D concentration is also inversely correlated with a number of health outcomes, including bone mineral density, risk of hip fracture, incident cancer, and cardiovascular events. Therefore, circulating 25(OH)D concentration is used to define vitamin D sufficiency and deficiency. There is a known large variation across individuals and populations in circulating 25(OH)D concentration. Moreover, published trials demonstrate substantial heterogeneity in the biologic response to vitamin D treatment, defined by changes in parathyroid hormone (PTH), intestinal calcium absorption, bone turnover, and bone mineral density.⁴⁷ While clinical characteristics such as race (presumably due to differences in cutaneous vitamin D production due to skin pigmentation), sun exposure, dietary intake of vitamin D, and adiposity (presumably due to vitamin D volume of distribution/fat sequestration) are known to be associated with circulating 25(OH)D concentration, they explain a minority of this variation. Additional reasons for differences in 25(OH)D and the 25(OH)D response to supplementation are poorly understood.

Vitamin D clearance plays an important role in vitamin D biology. Concentrations of vitamin D metabolites in blood and tissues must necessarily represent a balance of production and clearance. In health, CYP24A1 is the major enzyme responsible for catabolism of both 25(OH)D₃ and 1,25(OH)₂D₃ (**Figure 1**).^{4,48-54} CYP24A1 is found in most tissues in the body and is rapidly induced by 1,25(OH)₂D₃ to prevent 1,25(OH)₂D₃ intoxication.⁵⁵⁻⁵⁷ Polymorphisms in CYP24A1 were found to be associated with circulating 25(OH)D concentration in a genome-wide association study (GWAS).⁵⁸ Similarly, in another GWAS, a polymorphism in CYP24A1 showed the strongest association with the circulating concentration of PTH, a hormone known to regulate and be regulated by 1,25(OH)₂D.⁵⁹ In unpublished data, we found a CYP24A1 polymorphism to also be most strongly associated with the serum concentration of fibroblast growth factor-23, another hormone known to regulate and be regulated by 1,25(OH)₂D. Inactivating mutations in CYP24A1 have been found to cause “idiopathic” infantile hypercalcemia, characterized by excess 1,25(OH)₂D-mediated intestinal calcium absorption and hypercalcemia,

particularly with vitamin D supplementation.⁴⁹ These observations demonstrate that vitamin D clearance is critical for maintaining proper vitamin D and calcium homeostasis, perhaps most crucially in the context of vitamin D supplementation.

Serum 24,25(OH)₂D₃ (or its ratio with 25(OH)D₃) maybe a useful novel biomarker of functional vitamin D status. Because CYP24A1 is found in most tissues in the body and is rapidly induced by 1,25(OH)₂D₃,⁵⁵⁻⁵⁷ CYP24A1 expression is commonly used as a marker of tissue 1,25(OH)₂D₃ activity in basic science.⁶⁴⁻⁸⁰ However, the ability of vitamin D catabolism to reflect 1,25(OH)₂D₃ function has not been similarly harnessed for clinical use. Evaluation of circulating 24,25(OH)₂D₃ concentration may offer this opportunity. 24,25(OH)₂D₃ is the most abundant product of 25(OH)D₃ catabolism by CYP24A1.⁴⁹ When viewed in the context of prevailing 25(OH)D₃, 24,25(OH)₂D₃ reflects CYP24A1 activity. 24,25(OH)₂D₃ circulates at high concentrations (generally 1-10 ng/mL)^{81,82} and has a circulating half-life of approximately 7 days.⁸³ Circulating 24,25(OH)₂D₃ appears to come from both renal and non-renal sources.^{54,67,84-86} In the kidney proximal tubule, CYP24A1 transcription is induced by fibroblast growth factor-23 and suppressed by PTH.^{56,87} In our work, we have found chronic kidney disease (CKD, specifically low estimated glomerular filtration rate, or eGFR) to be strongly correlated with serum 24,25(OH)₂D₃ concentration.

Our preliminary data suggest that vitamin D supplementation increases vitamin D catabolism. We recently published a study assessing the effects of vitamin D₂ (ergocalciferol) supplementation on circulating vitamin D metabolites and vitamin D regulatory hormones.⁸⁸ We enrolled 25 participants with CKD

(eGFR <60 mL/min/1.73m²) and 44 participants with eGFR ≥60 mL/min/1.73m² and treated each with vitamin D₂ 50,000 IU twice weekly for 5 weeks. We measured vitamin D metabolites at baseline and the end of treatment using the precise mass spectrometry methods described in Section 4e of Approach. Among other findings, we reported that vitamin D₂ supplementation significantly increase serum 24,25(OH)₂D₃ to 25(OH)D₃ ratio (**Table 2.1**), suggesting induction of 25(OH)D₃ clearance. We hypothesized that induced clearance

2.1 Risk / Benefit Assessment

This study will not provide any direct benefit to the study subjects. Individual subjects may have a modestly reduced chance of adverse health events because their care will be monitored more closely than it might otherwise. Future patients may benefit from these studies by virtue of knowledge gained about the pathophysiology and ascertainment of impaired vitamin D metabolism.

The risks of administering deuterated 25(OH)D₃ in tracer quantities are low. 25(OH)D₃ is a naturally occurring substance and generally circulates in concentrations of 10-50 ng/mL. The deuterated 25(OH)D₃ we propose to administer differs from the naturally occurring form only by the substitution of 6 hydrogen atoms with deuterium. This isotope is stable and has metabolic and biologic characteristics identical to the naturally occurring form. We will administer quantities intended to make small changes in total circulating 25(OH)D₃ concentration, i.e., an increase of 5 ng/mL.

There is some risk of hypercalcemia with the administration 25(OH)D₃, but this risk is minimized by excluding participants with baseline 25(OH)D > 50 ng/mL and by administering quantities that raise 25(OH)D by only approximately 5 ng/mL. We will monitor for hypercalcemia during our research. If instances of hypercalcemia are observed, we will change our study protocol accordingly to prevent hypercalcemia in future participants. Moreover, this protocol will only enroll participants who successfully completed a related protocol (CLEAR or CLEAR-CF) without adverse effect. This study also includes placement of peripheral intravenous catheters and blood draws. Risks include discomfort at the site of administration, minor bleeding associated with catheter placement, and anemia due to blood sampling.

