6.2 Inclusion Criteria

The main inclusion criterion is the successful completion of related protocol CLEAR or CLEAR-CF, defined as:

- Receipt of D₆-25-hydroxyvitamin D₃ Solution under the CLEAR or CLEAR-CF protocol,
- Completion of at least 7 CLEAR or CLEAR-CF study visits, and
- Absence of adverse events related to D₆-25-hydroxyvitamin D₃ Solution administration during participation in CLEAR or CLEAR-CF

CLEAR and CLEAR-CF enrolled only adults, with additional eligibility criteria related to race, disease status (stage of chronic kidney disease or presence of cystic fibrosis), and screening serum 25(OH)D concentration (10-50 ng/mL).

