10.2 Re-screening Visit (Study Visit 1)

The Re-screening Visit will take place approximately 90 days after the Screening Visit (allowable range 60-180 days). The following activities will occur during the re-screening visit:

- Confirm adherence ($\geq 80\%$) to study vitamin D₃ (by self-report and pill count)
- Repeat focused medical history restricted to study eligibility criteria
- Complete medication inventory through EMR and patient report.
- Physical Exam (height and weight), and Vital Signs (blood pressure, heart rate)
- Collect non-fasting blood sample for measurement of complete blood count and total 25(OH)D.
- Collect non-fasting blood sample for serum sodium, potassium, chloride, bicarbonate, random glucose, BUN, creatinine, AST/SGOT, ALT/SGPT, albumin, calcium, and phosphorous.
- Participants who continue to meet eligibility criteria, at the screening visit and who are adherent ($\geq 80\%$) to study vitamin D₃, will be invited to return for the remaining study visits.
- Provide selected subjects with supplies required for first 24-hour urine collection

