10.3 Baseline Visit (Study Visit 2, Day 0)

Visit 2 will take place at the University of Washington Clinical Research Center (CRC) or a suitable alternate facility and will last approximately 5 hours. Visit 2 will take place at least 90 days after Visit 0 and no more than 90 days after Visit 1. If more than 90 days elapse between Visits 1 and 2, screening procedures may be repeated to verify continued eligibility. The following activities will occur during the baseline visit:

- Perform a complete medical history
- Review current medications.
- Physical Exam (height and weight), and Vital Signs (blood pressure, heart rate)
- Complete physical activity and food frequency questionnaires.
- Pregnancy test for women of childbearing potential
- Collect blood **prior to administration of study drug** for measurement of basic chemistries, vitamin D metabolites, parathyroid hormone (PTH), and other measurements related to kidney disease and vitamin D metabolism.
- Collect urine sample from first 24-hour collection period. Sample will be used for measurement of albumin, creatinine, vitamin D binding protein, and vitamin D metabolites:
- Administer D₆-25(OH) D₃ intravenously.

- Collect blood 5 minutes and 4 hours post-infusion for measurement of vitamin D metabolites.
- Distribute supplies for second 24-hour urine collection.

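### Section 6.3 and Table 6.3 give the hemoglobin exclusion in mg/dL instead of g/dL, so as written it excludes nobody; section 2.1 also needs to say when its 25(OH)D limit was applied

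*Combined protocol and SAP*

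**What the plan says.** **Hemoglobin.** The synopsis exclusion criteria set the limit at below 9 g/dL. The list in section 6.3 and the summary in Table 6.3 both set it at below 9 mg/dL. Section 9.2.1 places the complete blood count at the re-screening visit. Section 2.1 names anemia from blood sampling among the risks, and Appendix 2 totals the blood drawn at 143 mL.

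**25(OH)D.** Section 2.1 says of hypercalcemia after the tracer that "this risk is minimized by excluding participants with baseline 25(OH)D > 50 ng/mL", and adds that the dose is small. Section 6.2 reports that CLEAR and CLEAR-CF had their own eligibility criteria, including "screening serum 25(OH)D concentration (10-50 ng/mL"). The synopsis exclusions, section 6.3 and Table 6.3 contain no 25(OH)D limit.

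Vitamin D3 2000 IU daily is prescribed at Visit 0 (section 10.1). At re-screening the plan is to "Collect non-fasting blood sample for measurement of complete blood count and total 25(OH)D". The rule for continuing refers to "Participants who continue to meet eligibility criteria, at the screening visit and who are adherent" to at least 80%. The tracer is given at Visit 2, Day 0, which section 10.3 calls the Baseline Visit: "Visit 2 will take place at least 90 days after Visit 0 and no more than 90 days after Visit 1".

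**The concern.** Sections 6.3 and Table 6.3 are the lists that staff apply. An exclusion limit there decides who goes on to tracer dosing and repeated blood draws. A limit that no living person could fail is no safeguard, and it disagrees with the synopsis of the same document. Anyone auditing eligibility would have two limits to choose between.

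The 25(OH)D sentence raises a milder question of the same kind. A reader of section 2.1 may take it that nobody above 50 ng/mL receives the tracer. Staff following sections 6.3 and 10.2 have no such rule: a re-screening result of, say, 55 ng/mL has no action attached. The risk section and the operating rules should describe the same protections.

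**Working it through.** **1. Hemoglobin unit**

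- Inputs: 9 g/dL (synopsis); 9 mg/dL (section 6.3 list); 9 mg/dL (Table 6.3).
- Conversion: 1 g/dL = 1000 mg/dL, so 9 mg/dL = 9 / 1000 = 0.009 g/dL.
- Ratio of the synopsis limit to the section 6 limit: 9 / 0.009 = 1000.
- The mg/dL unit appears in two separate places in section 6, so a single misread character is an unlikely explanation.

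**2. Blood volume to which the limit is relevant (Appendix 2)**

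- By visit: 11 + 48 + 10 + 10 + 14 + 5 × 10 = 143 mL.
- By sample type: 3 + 12 + 4 + 114 + 10 = 143 mL. The two totals agree.
- The complete blood count is taken at re-screening, where 11 mL is drawn. The volume drawn after that check is 143 − 11 = 132 mL.

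**3. Where a 25(OH)D limit applies**

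| Place | 25(OH)D limit? |
|---|---|
| Section 2.1 | Asserted: above 50 ng/mL at baseline excluded |
| Section 6.2 | 10-50 ng/mL, as a past screening criterion of CLEAR/CLEAR-CF |
| Synopsis exclusions | None |
| Section 6.3 and Table 6.3 | None |
| Section 10.2, rule for continuing | None; eligibility criteria and at least 80% adherence |

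The parent-study measurements were un-supplemented. At least 90 days pass between prescription of the supplement and the tracer, so at least 2000 × 90 = 180,000 IU has been prescribed by then. Section 10.3 sets no firm upper end to the interval: "If more than 90 days elapse between Visits 1 and 2, screening procedures may be repeated to verify continued eligibility". The protocol itself says "Serum or plasma 25(OH)D concentration increases robustly to vitamin D supplementation or exposure to ultraviolet light". A parent-screening value therefore does not establish the level at dosing.

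A starting range of 10 to 50 ng/mL leaves 40 to 0 ng/mL of room below 50. The documents give no conversion from IU to ng/mL, so the number of participants who would exceed 50 ng/mL cannot be derived, and none is estimated here.

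**4. Which hypercalcemia protections operate at dosing**

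- Serum calcium above 10.1 mg/dL is an exclusion (synopsis, section 6.3, Table 6.3).
- Calcium is checked at re-screening, before the tracer (section 7).
- Calcium is repeated at Baseline and Day 7 (section 9.2.2).
- The dose targets a rise of about 5 ng/mL, and all participants have had the tracer before without related adverse events.

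Section 2.1 mentions the small dose, the earlier tolerance, monitoring for hypercalcemia, and changing the protocol if hypercalcemia occurs. It does not mention the calcium exclusion.

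**The case against.** On hemoglobin, the best defense is that this is an evident slip: the synopsis has the right unit, and no clinician would apply 0.009 g/dL. That probably describes what happens at the site. It limits the practical harm but does not make the criterion correct, because the error stands in both operative lists and the document contradicts itself.

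On 25(OH)D, the defense is stronger. Section 14.6 uses baseline for the un-supplemented state, contrasting baseline with supplemented clearance. On that usage section 2.1 is true: every participant passed the 50 ng/mL limit at parent-study screening. This stands, and section 2.1 should not be called false. The remaining difficulty is that section 10.3 uses Baseline for Day 0, after the run-in, and that on the favorable reading the limit does not describe the level when the tracer is given.

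A reader might infer that participants face an unguarded hypercalcemia risk. The documents do not support that, because calcium is an exclusion in its own right and is checked on supplement before dosing. A reader might also infer that the paired comparison of clearance is compromised. It is not: no 25(OH)D selection is applied at dosing under the current rules.

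**Conclusion.** The hemoglobin limit in section 6.3 and Table 6.3 is wrong as written, by a factor of 1000, and should be corrected. This assumes that the synopsis value of 9 g/dL is the intended one; a limit of 0.009 g/dL has no sensible purpose.

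The 25(OH)D sentence is a minor clarification. It is either inaccurate for this study (baseline as Day 0) or accurate but uninformative about the level at dosing (baseline as the un-supplemented state). Neither reading shows harm to participants or an effect on the primary analysis or sample size.

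It may be tempting to conclude that a 50 ng/mL cap should be imposed at dosing. The documents do not support that as a correction. Section 1 says steady-state 25(OH)D depends on clearance, so a cap would tend to remove people with low clearance, which is the primary outcome. A cap applied at re-screening would not fix the level at dosing either, since Visit 2 may follow by up to 90 days of further supplementation, or longer if screening is repeated.

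**What to change.** 1. In section 6.3 and Table 6.3, change the hemoglobin exclusion to < 9 g/dL, matching the synopsis.
2. In section 2.1, replace the 25(OH)D clause with wording such as: all participants had 25(OH)D of 10-50 ng/mL when screened for CLEAR or CLEAR-CF, before supplementation, and this study applies no 25(OH)D limit; protection at dosing rests on excluding serum calcium > 10.1 mg/dL at re-screening, on calcium measured at Baseline and Day 7, and on a tracer dose expected to raise 25(OH)D by about 5 ng/mL.
3. In section 10.2, add a sentence saying whether the re-screening 25(OH)D result is only recorded or acted on, and how.

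The cost is a text amendment with no new visit, tube or assay. The hemoglobin correction would change who is enrolled only if the site had been applying the mg/dL limit literally; in that case the people newly excluded are those the synopsis already meant to exclude. No 25(OH)D cap is proposed.
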